Title	A pilot study investigation the effects of cross frequency transcranial alternating current stimulation on cortical oscillations underlying cognition
Short Title	2PAC
Protocol Number	Version 3.0
Phase	Pilot
Methodology	Double-blind, randomized, active sham controlled
Study Duration	This study will take two months to complete.
Study Center(s)	This is a single-site study performed at the University of North Carolina at Chapel Hill.
Objectives (Purpose)	The primary objective of this study is to explore the effect of transcranial random noise stimulation on oscillations underlying cognition
Number of Subjects	24
Diagnosis and Main Inclusion Criteria	Eligible participants will be healthy adults between the ages of 18-35 with no history of mental or psychiatric disorder.
Description of Intervention (Procedures/methods)	The participants will be randomized into one of three arms: either 40 minutes of sham tACS or 40 minutes of theta-gamma tACS or 40 minutes of delta-beta tACS while performing a cognitive control task.
Related IRB Applications	N/A

1.4 FUNDING SOURCES

Please list below the funding sources for this project:

Sponsor Name	UNC Ramses Number	Sponsor Type	Prime Sponsor Name	Prime Sponsor Type	Sponsor/Grant Number
N/A	N/A	N/A	N/A	N/A	N/A

External Funding: This project is not externally funded.

UNC-CH Funding: This project is not funded through UNC-CH.

Classified: This project is not classified.

2 INTRODUCTION

This document is a protocol for a human research study. This study is to be conducted according to U.S. and international standards of Good Clinical Practice (FDA Title 21 Part 312 and International Conference on Harmonization guidelines), applicable government regulations and Institutional research policies and procedures.

2.1 BACKGROUND

Noninvasive brain stimulation (NIBS) methods have recently been gaining acceptance and attention as treatment strategies for many neurological and psychiatric disorders as well as improving cognition. The methods include well studied methods such as transcranial magnetic stimulation (TMS) and transcranial direct current stimulation (tDCS) as well as novel methods like transcranial alternating current stimulation (tACS), transcranial random noise stimulation (trNS) and cross-frequency transcranial alternating current stimulation (CF-tACS). In particular, CF-tACS has been used to improve working memory capacity (Alekseichuk et al. 2017). CF-tACS was designed to target naturally occurring cross-frequency electrical coupling that is witnessed in a variety of cognitive tasks, such as episodic memory encoding (Poeppel et al. 2016), decision-making (Arnal et al. 2015), and attention (Quax et al. 2017). Recent evidence has even suggested that cross-frequency coupling underlies the relief from the symptoms of Parkinson's disease experience by patients with chronically implanted deep brain stimulators (deHemptinne et al. 2015). Cross-frequency coupling of neural oscillations is a relatively novel model of brain activity that has been gaining empirical traction over the past decade (see Canolty & Knight 2010 for review).

Oscillations are periodic electrical activity observed both intracranially and transcranially in humans using electrocorticograms (ECoG), electroencephalograms (EEG), magnetoencephalograms (MEG) (Buzsaki, Anastassiou, & Koch, 2012). Oscillations have been demonstrated to modulate neuronal firing, organize communication within and between brain regions and hence coordinate cognition (Fries, 2005; [name] & McCormick, 2010; Jensen & Mazaheri, 2010). Oscillations in the frequency bands 4 – 8 Hz and 8 – 12 Hz (often referred to as theta and alpha band) have been shown to be correlated with working memory performance (Jensen, Gelfand, Kounios, & Lisman, 2002; Jensen & Tesche, 2002; Raghavachari et al., 2001) and cognitive control (Cavanagh & Frank, 2014). Thus, changes in cognitive performance could be reflected in changes in oscillations. The current study aims to test for the role of cross-frequency coupling in cognitive processes.

We will be collecting a saliva sample at the first session. This sample will be used to test for a single nucleotide polymorphism in the BDNF gene whose presence may have an influence on effectiveness of brain stimulation. Within the central nervous system, BDNF regulates survival, proliferation, and synaptic growth as well as directly influences synaptic plasticity in the adult human brain (Antal et al., 2010). Egan et al. (2003) demonstrated that Val66Met, a single nucleotide in the BDNF gene, has function consequences in healthy humans, including decreased episodic memory and hippocampal inducing a reduction in recall capacity. This polymorphism is common in over one third of the Caucasian population (65% Val66Val to 35% Val66MET) (Pezawas et al, 2004; Hariri and Weinberger, 2003). Kleim et al. (2006) found that individuals with the Val/Val polymorphism respond to tDCS and transcranial magnetic stimulation (TMS) treatments with expected change, whereas, individuals expressing Val/MET allele do not. These authors indicate the difference to be caused by the impairment in synaptic plasticity caused by the Val/MET allele. These findings suggest that individual efficacy of treatments using brain stimulation may be partially genetically predetermined and should be taken into account when performing such procedures. Accordingly, we will conduct genotyping of all participants in this study in order to assess BDNF status.

In addition to BDNF, we will be assessing sex hormone levels in our participants before stimulation. Cortical excitability has been shown to depend on the phase of the menstrual cycle in women (Smith et al. 1999, Badawy et

al. 2013, Walpurger et al. 2004). This effect may be mediated by sex hormones (e.g., estradiol, progesterone, testosterone, androstenedione). To account for the different levels of sex hormones in participants when they arrive for the experimental sessions, we will collect saliva for assessing levels of estradiol, progesterone and testosterone. In addition, we will ask women information on birth control use and the best guess-estimate of first day of last menstrual cycle.

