5.2 STIMULATION SESSIONS

Participants will undergo four sessions with the same procedure; the only change will be the stimulation condition. In the initial session, participants will have the procedure explained and reminded of their expectations and rights (informed consent). After obtaining consent, a urine drug test and pregnancy screening will be administered. Sessions 2, 3, and 4 will be the same as session 1, except there will be no CF-tACS stimulation during session 1.

5.4.1 SESSION 1

In the initial session, participants will be explained the procedure and reminded of their expectations and rights (informed consent). After obtaining consent, a urine drug test and pregnancy screening will be administered.

- Preparation - Once a negative pregnancy test and negative drug test are confirmed, the stimulation electrodes, EEG net, ECG electrodes and respiration belt will be applied.
- Questionnaires - The participant will fill out a series of questionnaires pertaining to self-reported handedness, affect, behavioral traits and sleep quality.
- Saliva collection - Saliva will be collected for BDNF genotyping and sex hormone level measurement.
- Resting state EEG – Participant will be asked to relax with eyes open and EEG will be collected simultaneously
- Practice cognitive tasks - The participant will perform a shortened version of the cognitive tasks as practice from which baseline performance will be assessed.

· Following the practice, the participant will receive 40 minutes of either verum CF-tACS or sham CF-tACS stimulation, depending on the randomized condition. During the stimulation, the following procedures will be followed

A. Cognitive Control Task – Participant will perform a cognitive control task for 5 minutes. CF-tACS will be delivered during these 5 minutes. There will be no CF-tACS during session 1.

B. Resting state EEG - Participant will be asked to relax with eyes open and EEG will be collected simultaneously for 3 minutes. There will be no CF-tACS during this time. Subject are allowed to take more (but not less) than 3 minutes of rest if desired.

- Repeat steps A and B 8 times until all conditions of the Cognitive Control Task are finished

Following the end of stimulation,

- Electrodes and net will be removed and participant can wash their hair and face

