12.2 STATISTICAL ANALYSIS PLANS

Statistical analyses will be performed to test the null hypothesis indicated in section 2.4 *Study Aims/Hypothesis*.

The cognitive task will consist of 400 trials. The EEG recorded simultaneously with the task will be analyzed following an established preprocessing pipeline to remove artifacts related to eye movements, eye blinks, heart beats and muscle activity. The oscillation power and phase will be estimated using Morlet wavelet convolution. The primary outcome is phase-amplitude coupling between the stimulated frequencies (measured from EEG), reaction time, and accuracy. Phase amplitude coupling will be calculated as the phase locking value corrected for spurious noise using a boot-strapped null distribution (see Cohen Analyzing Neural Time Series Data 2014 for method).

Our primary outcomes and their test are described below:

- Theta-gamma tACS will increase theta-gamma phase amplitude coupling (one-tailed, Student's t-test)
- Delta-beta tACS will increase delta-beta phase amplitude coupling (one-tailed, Student's t-test).
- Theta-gamma tACS will alter behavior (reaction time or accuracy) as a function of set-size relative to sham-tACS (Student's t-test).
- Delta-beta tACS will alter behavior (reaction time or accuracy) as a function of abstraction relative to sham-tACS (Student's t-test).

As exploratory analysis, linear mixed-effects models with BDNF genotype, sex hormone levels, as factors in addition to the variables condition and period will be fit with the rest of the analysis following what is described for primary analysis.

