APPENDIX A: SCHEDULE OF EVENTS

	Phone Screening	Session 1	Sessions 2,3,4 with Stimulation
Procedures			
Provide Verbal Consent	x		
Signed Consent Form		x	
Assessment of Eligibility Criteria	x	x	
Urine Pregnancy Test		x	
Urine Drug Test		x	
Baseline Assessments (BIS/BAS, Handedness, STAI, PSQI, BDI,P ANAS)		x	
Saliva Collection		x	
Baseline EEG (Resting state)		x	x
Task EEG (Cognitive task with intermittent resting-state)		x	x
Stimulation during task			x
Stimulation Questionnaire			x

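### Sex hormones are meant to account for levels at the stimulated sessions, but the schedule samples saliva only at the unstimulated Session 1, so as a main effect the value cannot adjust for session-to-session variation (minor)

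*Combined protocol and SAP*

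**What the plan says.** Section 2.1 motivates the hormone assay with a factor that varies over time: "Cortical excitability has been shown to depend on the phase of the menstrual cycle in women". It gives the purpose as "To account for the different levels of sex hormones in participants when they arrive for the experimental sessions". It adds that women will be asked about contraceptive use and roughly when their last period began, without saying when they are asked or how the answers will be analysed.

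On timing:

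- Section 2.1 opens its saliva paragraph with "We will be collecting a saliva sample at the first session", in a sentence that introduces the BDNF sample.
- The Session 1 list in Section 5.2 states "Saliva will be collected for BDNF genotyping and sex hormone level measurement". The same list states "There will be no CF-tACS during session 1".
- Appendix A has one row, "Saliva Collection", marked under Session 1 and blank under Sessions 2, 3 and 4.
- Section 5.2 also says that "Sessions 2, 3, and 4 will be the same as session 1", apart from the absence of stimulation at Session 1.

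On use, Section 7.3 lists hormone level among the exploratory covariates for differences in spectral power. Section 12.2 plans, as exploratory work, "linear mixed-effects models with BDNF genotype, sex hormone levels, as factors", alongside condition and period.

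**The concern.** The stated reason for measuring hormones is that they may differ from one visit to the next and so affect the response to stimulation. A sample from a single visit does not measure that, and under Appendix A the visit sampled is the one without stimulation. The conditions are compared within participants across Sessions 2, 3 and 4, so only a covariate that changes across those sessions can, as a main effect, remove hormone-related variation from the comparison.

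What is at stake is the exploratory model and what it yields for planning. Aim 3 in Section 2.4 is to obtain parameter estimates for a later study. Under Appendix A there would be no estimate of session-level hormone effects. Staff also have two instructions about saliva at Sessions 2, 3 and 4 that cannot both be followed, and a sample not taken cannot be recovered.

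**Working it through.** The plan gives no figure on this point to reproduce. The check has three steps.

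**1. Lag between sample and stimulated sessions.** Section 4 gives four visits at least 1 week apart. With the sample at Session 1, the minimum lags are:

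- Session 2: 1 × 7 = 7 days
- Session 3: 2 × 7 = 14 days
- Session 4: 3 × 7 = 21 days

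If a cycle of about 28 days is assumed (the documents give none), these are 7/28, 14/28 and 21/28, or a quarter, a half and three quarters of a cycle. They are minimum lags, and the fractions apply only to women who are cycling. The number of such women is not given.

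**2. What a once-measured covariate can add.** Take Section 4's design: 24 participants, three stimulated periods and six sequences, so 24 × 3 = 72 observations. With participant, period and condition effects, the rank of the design matrix is

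1 (intercept) + 23 (participants) + 2 (periods) + 2 (conditions) = 28.

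| Covariate added | Rank | Within-participant information added |
|---|---|---|
| None | 28 | – |
| One Session 1 value per participant, main effect | 28 | None |
| A separate value at each stimulated session, main effect | 29 | One term |
| Session 1 value with its interaction with condition | 28 + 2 = 30 | Two terms, as a modifier of the condition effect |

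The second row follows because a value constant across a participant's three periods is a linear combination of the participant indicators. It needs no assumption about the size of any hormone effect.

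**3. Illustration of the precision at stake.** Assumptions, not taken from the documents: hormone slope 0.5 per SD, residual variance 1, hormone values independent between sessions. The expected within-participant residual variance without adjustment is 1 + 0.5² = 1.25. Averaged over 300 simulated trials of this design, the residual variance was:

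- no covariate: 1.26
- Session 1 value as a main effect: 1.26
- session-specific values: 1.00

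The fall from 1.26 to 1.00 depends wholly on the assumed slope and independence. The absence of any fall with the Session 1 value does not.

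**The case against.** Four points can be made for the plan.

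*The value is not useless.* A reader might infer that a Session 1 hormone level cannot explain any difference between a participant's sham and active sessions. The documents do not support that. Section 7.3 speaks of differences in spectral power. If these are active-minus-sham differences, a participant-level value can explain why the stimulation effect varies between people. In the mixed model this is the hormone-by-condition term, which raises the rank from 28 to 30. Section 12.2 does not write that term down, but does not exclude it. This stands, and it limits the point to the main effect.

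*Saliva may be intended at every session.* Section 5.2's general sentence would allow that. It is weak evidence, because Appendix A marks the urine tests at Session 1 only and Section 3.2 makes later pregnancy tests conditional, so the sentence is not applied literally elsewhere. What is established is an unresolved conflict, not proof that the samples will be missed.

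*Section 2.1 may mean differences between participants.* Hormones are introduced next to BDNF, a fixed trait. The wording permits this reading, but the menstrual-phase rationale and the plural reference to sessions count against it.

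*Cycle information is already collected.* One menstrual date combined with the visit dates would give an approximate cycle day later on. That is true, but no planned analysis uses it.

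**Conclusion.** The point holds in a limited form and is minor. Section 2.1's purpose and Appendix A's schedule do not match, and Section 5.2 contains text on both sides. If Appendix A is followed, the hormone main effect contributes nothing to the within-participant comparison of conditions (rank 28 to 28). The value can act only between participants or as a modifier of the stimulation effect.

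A reader might go on to infer that the sham comparison is biased or that the primary results are affected. Neither follows. Hormones enter only the exploratory analyses in Sections 7.3 and 12.2; the four primary t-tests and the sample size in Section 12.3 do not use them. Condition order is randomised over six sequences, so hormone variation between sessions adds noise to the comparison and not systematic error. The cost is some lost precision in an exploratory model. Its size cannot be stated from the documents, and the menstrual-phase argument concerns only the cycling women enrolled.

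**What to change.** 1. Reconcile Section 2.1, Section 5.2 and Appendix A so that they agree on when hormone saliva is taken and what it is for.
2. At each of Sessions 2, 3 and 4, record the date the last period began and current contraceptive use, and add both items to Appendix A. In women who are cycling, enter cycle day at each session as a time-varying covariate in the exploratory mixed model. State its coding in advance, including how men and women who are not cycling are handled.
3. Describe the Session 1 hormone value as a participant-level modifier, and write the hormone-by-condition term into Section 12.2.

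The cost is two questions per session (2 × 3 = 6 per woman), an amended schedule table and a few sentences in the plan.

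Hormone saliva at the stimulated sessions is optional and not needed for this fix. It would mean 3 × 24 = 72 assays in place of 24. Section 6.4.2 already has samples frozen and assayed after data collection, so extra samples could be stored and the assay decision deferred.

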2.2 INVESTIGATIONAL AGENT

CF-tACS involves the application of electric current on the scalp in a waveform that emulates the coupling between two frequencies: a higher frequency waveform is nested in the peak of lower frequency waveform (Alekseichuk et al., 2016) and has previously been demonstrated to increase performance during a working memory task.

2.3 DOSE RATIONALE

The primary rationale for the dose is the duration of the cognitive tasks that we require the participants to perform during stimulation. The task takes about 40 minutes total and is broken up into 8 blocks. The activity from the brain is unable to be accurately recorded during the stimulation itself, so we have included resting-state periods after each block of the task with stimulation to allow for analysis of brain activity (see Alekseichuk et al., 2016 for similar methods). Moreover, our lab has successfully performed many transcranial electrical stimulation experiments where stimulation duration has been 40 minutes (IRB # 14-1622, 16-1911) and no significant side effects have been observed.

2.4 STUDY AIMS/HYPOTHESES

The purpose of this pilot study is to evaluate the potential efficacy of using CF-tACS to modulate cortical oscillations observed during cognitive tasks, to generate hypotheses, and to obtain statistical estimates and other information needed for planning a subsequent larger-scale study.

Aim 1. Characterize CF-tACS effects in terms of the outcome measures of interest.

Aim 2. Perform exploratory analyses to generate new hypotheses.

Aim 3. Obtain preliminary data and population parameter estimates needed to plan a future study.

3 SUBJECT SELECTION AND WITHDRAWAL

A total of 24 participants will be recruited for this study and all data will be collected at UNC-CH. No specific plans have been made to enroll participants from vulnerable populations.

3.1 INCLUSION CRITERIA

In order to be eligible to participate in this study, a participant must meet all of the following criteria:

- Between the ages of 18 and 35 years
- Able to provide informed consent
- Willing to comply with all study procedures and be available for the duration of the study
- Speak and understand English

3.2 EXCLUSION CRITERIA

A potential participant who meets any of the following criteria through self-report will be excluded from participation in the study:

- ADHD (currently under treatment)
- Neurological disorders and conditions, including, but not limited to:
 - History of epilepsy
 - Seizures (except childhood febrile seizures and ECT-induced seizures)
 - Dementia
 - History of stroke
 - Parkinson's disease
 - Multiple sclerosis
 - Cerebral aneurysm
 - Brain tumors
- Medical or neurological illness or treatment for a medical disorder that could interfere with study participation (e.g., unstable cardiac disease, malignancy)
- Prior brain surgery
- Any brain devices/implants, including cochlear implants and aneurysm clips
- History or current traumatic brain injury
- (For females) Pregnancy or breast feeding
- Personal or family history of mental/psychiatric disorder (e.g., anxiety, major depressive disorder, schizophrenia, etc.)
- Positive urine test for the following: Marijuana (THC), Cocaine (COC), Phencyclidine (PCP), Amphetamine (AMP), Ecstasy (MDMA), Methamphetamine (Mamp), Opiates (OPI), Oxycodone (OXY), Methadone (MTD), Barbiturates (BAR), Benzodiazepines (BZO), Buprenorphine (BUP), Tricyclic Antidepressants (TCA), Propoxyphene (PPX)
- Anything that, in the opinion of the investigator, would place the participant at increased risk or preclude the participant's full compliance with or completion of the study

Justifications for any exclusions based on race, gender, or ethnicity: There are no exclusion criteria based on race, gender, or ethnicity. However, non-English speaking individuals are excluded because the ability to accurately and

completely communicate study information, answer questions about the study, and obtain consent are necessary. This may skew enrollment away from Hispanic/Latino population.

Justification for excluding women or women who become pregnant: Pregnant participants will be excluded out of an abundance of caution despite the fact that theoretical risk to mother or fetus is exceedingly small, since no safety data for pregnancy are known to exist for CF-tACS studies and only limited safety data for other noninvasive brain stimulation methods like TMS (Sayar et al. 2014) . We will verify pregnancy status via a urine pregnancy test for all female participants prior to receiving treatment on Day 1 of Stimulation.

At the beginning of Sessions 2, 3 and 4, female participants will be asked if there is a possibility that they might be pregnant since Session 1. If the participants answer 'Yes' or 'Maybe', pregnancy test will be conducted. A pregnancy questionnaire will be used to document the answers.

Sayar, G. H., Ozten, E., Tufan, E., Cerit, C., Kaan, G., Dilbaz, N., & Tarhan, N. (2014). Transcranial magnetic stimulation during pregnancy. *Archives of women's mental health*, 17(4), 311-315.

